## 5 Statistical Analysis/Calculations

## 5.1 Primary Endpoints

## 5.1.1 Primary Safety Endpoint

The primary safety endpoint is the proportion of participants with freedom from CEC adjudicated device- or procedure-related SAEs through 30 days.

The primary safety endpoint will be evaluated against a PG of 82.6%, which was set with a 10% non-inferiority margin of the estimated 92.6% through 30 days derived from premarket data from the prior clinical investigations evaluating the WavelinQTM EndoAVF System.

The primary safety endpoint will be evaluated by the following hypothesis:

- H₀: The primary safety endpoint of proportion of AVF with freedom from SAE for the WavelinQTM EndoAVF System treated participants through 30 days (PWS) is less than or equal to that of the PG of 82.6%.
- H1: The primary safety endpoint of proportion of AVF with freedom from SAE for the WavelinQTM EndoAVF System treated participants through 30 days (PWS) is greater than that of the PG of 82.6%.

That is:

 $H_0$ :  $P_{WS} \le 82.6\%$  $H_1$ :  $P_{WS} > 82.6\%$ 

Rejection of the null hypothesis will signify that the 30-day safety of the WavelinQTM EndoAVF System is greater than the safety PG of 82.6%.

The device- or procedure-related SAE will be identified if:

On the Adverse Event Adjudication page, Serious (SAE) is checked as Yes, and Relationship to Study Device is or Relationship to Procedure is Possibly Related or Definitely Related.

The binary definition is shown as below:

- If the device or procedure-related SAE start date occurs before or on Day 30, the participant is considered as having an event.
- If the participant discontinued before the beginning of 30-day follow-up visit window (30-5 = Day 25) without having the device- or procedure-related SAE, the participant is considered not evaluable and will not be included in the analysis.
- Otherwise, if the participant is in the investigation without having the device-related SAE and has passed the 30-day follow-up visit by the cutoff date of database lock, the participant is considered as not having an event.

The primary safety analysis will be conducted based on evaluable participants only in the ITT population. A two-sided p-value will be derived based on an exact binomial test comparing to the PG of 82.6% and the 95% two-sided confidence interval (CI) will be provided using the Clopper-Pearson method. The WavelinQTM EndoAVF System will be considered to have achieved the safety objective and will reject the null hypothesis if the two-sided p-value is less than 0.05, equivalently, the lower bound of the 95% CI is greater than 82.6%. The primary safety analysis will be repeated on the PP population.

Additionally, as a supportive analysis, Kaplan-Meier (KM) analysis will be used to analyze the primary safety endpoint.

- If the device or procedure-related SAE occurs before or on Day 30, the participant is considered as having the event at the corresponding start date.
- If the participant was transferred to PD, or had a kidney transplant, or had permanent abandonment, or had access discontinuation, or discontinued before Day 30 without having device or procedure-related SAE, the participant is considered as censored at the earliest date among these events (i.e., PD start date, kidney

transplant date, date of permanent abandonment, date of access discontinuation, last date of available study data including the unscheduled visit date).

• Otherwise, if the participant did not have a device or procedure-related SAE and has passed Day 30 by the cutoff date of database lock, the participant will be censored at Day 30 for this analysis.

The analysis will be evaluated on the ITT population. The number of participants with events, number of participants censored, time to event (days), and proportion of participants with events along with the 95% CI will be presented.

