6.4 Participant Follow-Up

6.4.1 Follow-Up Intervals and Methods

All participants are to be followed according to the investigational site's SOC practices. In addition to the SOC visits, treated participants will have an investigation follow-up visit at 30-days and 6-weeks as well as 6- and 12-months post index procedure and will have a phone call follow-up at 3-, 18- and 24-months. For participants into whom the WavelinQTM EndoAVF System was introduced during the index procedure but procedure success was not achieved, only the follow up at 30-days will be completed and limited to the collection of safety events and interventions. This follow-up may be conducted by phone for these participants and investigation participation for these participants will end upon completion of this follow-up.

All follow-up must be performed by authorized delegated clinical investigation site team members. Follow-up windows will be calculated from the index procedure date. Refer to Section 1.3 for an overview of follow-up window time frames and requirements for each visit. The following data will be collected and documented on the appropriate eCRF for each follow-up unless otherwise specified for treated participants:

- DUS: A DUS assessment per the Ultrasound Guidelines must be performed at the follow-up visits at 30-days and 6-weeks for all treated participants and again at 6-and 12-months for participants not yet successfully dialyzing with the AVF created as part of this clinical investigation using 2-needle cannulation. The 6- and 12-month DUS are also required for participants that are using the AVF created as part of this clinical investigation but for whom procedure access was obtained at the wrist artery during the index procedure. The DUS for these participants will be limited to the examinations of the artery that was accessed during the index procedure. At minimum, images including the following characteristics are required and must be submitted to the Sponsor / Core Lab as per the details specified in the investigational site's regulatory binder:
 - o Arteries and veins of the AVF: Patency (including characterization of each stenosis, if present), and inner diameters. Brachial artery volume flow.
 - AV-anastomosis & juxta-anastomotic area: Patency (including characterization of each stenosis, if present).
 - o Cannulation veins: Patency (including characterization of each stenosis, if present) and inner diameters.

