7.3 Sample Size Considerations

The sample size for the study of one-hundred and fifty (150) treated participants was established to assure adequate power for the primary safety and effectiveness endpoints as

well as to result in a sufficient sample size (when accounting for attrition) for assessment of the secondary and exploratory endpoints, specifically for those that only apply to subsets of the overall population (i.e. the incident population and wrist arterial procedure access population).

- 1) *Primary Safety Endpoint* The proportion of participants with freedom from device-or procedure-related SAEs through 30 days (ITT Population).
 - Assumptions:
 - The freedom from device- or procedure-related SAE rate for AVFs created using the WavelinQTM EndoAVF System is estimated at 92.6% through 30 days based on pre-market data;
 - The PG is set at 82.6% using a 10% non-inferiority margin;
 - The rate of attrition through 30 days is assumed to be 10%; and
 - o The Type 1 error is 0.05 (two-sided).
 - Sample Size:
 - A sample size of 150 treated participants [135 evaluable] will give over 92.5% power with a two-sided type I error of 0.05 as calculated using PASS 2019 (One Proportion Exact Test).
- 2) Primary Effectiveness Endpoint Interventions Post Creation to Facilitate AVF Use and / or Maintain AVF Use (Facilitation and / or Maintenance Interventions) through the Timepoint of the 6-Month Follow-Up of the Last Active Treated Participant (AT Population)
 - Assumptions:
 - The number of interventions post creation to facilitate AVF use and / or maintain AVF use after AVF creation using the WavelinQTM EndoAVF System is estimated at 3.0 / PY, a conservative assumption based on pre-market data;
 - The PG is set at 5 / PY to align with the targets and recommendations of the 2019 update of the KDOQI Clinical Practice Guideline for Vascular Access of < 2 interventions to facilitate and < 3 interventions to maintain AVF use;
 - The rate of attrition through 6-, 12-, and 24-months, including lost to followup, death, and other clinical investigation premature withdrawals is assumed to be 20%, 40%, and 60%, respectively; and
 - o The Type 1 error is 0.05 (two-sided).
 - Sample Size:
 - O A sample size of 150 treated participants, yielding more than 100 PY by the time the last active treated participant completes their 6-month follow-up, will give over 99% power with a two-sided type I error of 0.05 as calculated using PASS 2019 (One-Sample Poisson Rate Test).

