7.7.3 Handling of Missing Data

Investigation endpoints may have missing data due to a participant's withdrawal of consent, the withdrawal of a participant by the PI, a participant loss to follow-up and the death of a participant. Data may also be missing from investigation endpoints due to deviations and / or missing data collection. It is important to minimize missing data by all means and to always record the reason for omission.

For the primary safety endpoint, a conservative approach will be used for the handling of missing data: If a participant has a specified event (device-related or procedure-related SAE), the participant will be included irrespective of if the participant prematurely discontinues prior to the 30 day timepoint; if a participant prematurely discontinues before 30 days without the occurrence of a specified event, the participant will be considered not evaluable and will not be included in the primary safety endpoint analysis.

For the primary effectiveness endpoint, the Poisson regression model will be used to analyze the data. In the Poisson regression model, missing data handling is a standard part of the analysis: If a treated participant prematurely discontinues prior to the data cut, that participant's study duration will be considered as the period of time between the index procedure and their premature discontinuation, and the corresponding number of facilitation and/or maintenance interventions in that specific duration will be used for analysis.

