8 SAFETY MONITORING AND REPORTING

The PI is responsible for the detection, documentation and reporting of events and any new information concerning reported events to the Sponsor that meet the criteria and definitions set forth in this section. These events will be collected for ITT participants and collection thereof will begin immediately following the start of the index procedure (defined to start at the time of the initial skin puncture to gain vessel access). Events occurring prior to the index procedure, will be documented as medical history. Events and the status thereof will be collected through the final investigation required participant follow-up visit or premature discontinuation.

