## 2.4 Sample Size

The sample size for the investigation of one-hundred and fifty (150) treated participants was established to assure adequate power for the primary safety and effectiveness endpoints as well as to result in a sufficient sample size (when accounting for attrition) for assessment of the secondary and exploratory endpoints, specifically for those that only apply to subsets of the overall population (i.e., the incident population and wrist arterial procedure access population).

- 1) Primary Safety Endpoint The proportion of participants with freedom from device- or procedure-related SAEs through 30 days (ITT Population).
  - Assumptions:
    - The freedom from device- or procedure-related SAE rate for AVFs created using the WavelinQTM EndoAVF System is estimated at 92.6% through 30 days based on pre-market data;
    - The PG is set at 82.6% using a 10% non-inferiority margin;
    - o The rate of attrition through 30 days is assumed to be 10%; and
    - o The Type 1 error is 0.05 (two-sided).
  - Sample Size:
    - o A sample size of 150 treated participants [135 evaluable] will give over 92.5% power with a two-sided type I error of 0.05 as calculated using PASS 2019 (One Proportion Exact Test).
- 2) Primary Effectiveness Endpoint Interventions Post Creation to Facilitate AVF Use and / or Maintain AVF Use (Facilitation and / or Maintenance Interventions) through the Timepoint of the 6-Month Follow-Up of the Last Active Treated Participant (AT Population)
  - Assumptions:
    - The number of interventions post creation to facilitate AVF use and / or maintain AVF use after AVF creation using the WavelinQTM EndoAVF System is estimated at 3.0 / PY, a conservative assumption based on pre-market data;
    - The PG is set at 5 / PY to align with the targets and recommendations of the 2019 update of the KDOQI Clinical Practice Guideline for Vascular Access of ≤ 2 interventions to facilitate and ≤ 3 interventions to maintain AVF use:
    - The rate of attrition through 6-, 12-, and 24-months, including lost to follow-up, death, and other clinical investigation premature withdrawals is assumed to be 20%, 40%, and 60%, respectively; and
    - o The Type 1 error is 0.05 (two-sided).
  - Sample Size:

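### For the 30-day safety endpoint the SAP excludes event-free leavers only before Day 25, the CIP before Day 30; those leaving on Days 25–29 are unclassified or count for the device

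*SAP*

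**What the plan says.** Both documents define the endpoint as freedom from CEC-adjudicated related SAEs through 30 days, tested exactly against 82.6% (CIP 7.4.2, SAP 5.1.1). They differ on who is evaluable.

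- **CIP 7.7.3:** "if a participant prematurely discontinues before 30 days without the occurrence of a specified event, the participant will be considered not evaluable". Participants with an event stay in whenever they leave. The section describes this approach as conservative.
- **SAP 5.1.1, primary analysis:** there are three rules. A related SAE starting by Day 30 is an event. The second rule, for event-free leavers, opens "If the participant discontinued before the beginning of 30-day follow-up visit window (30-5 = Day 25") and makes only those participants not evaluable. The third counts the remainder as event-free if they are in the investigation and past the 30-day visit at the data cut-off. It names device-related SAEs only.
- **SAP 5.1.1, supportive Kaplan-Meier analysis:** an event-free participant who discontinues before Day 30 is censored.

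The 30-day visit has a window of ±5 days (CIP 1.3). For participants in whom the device was introduced without procedure success it is the only follow-up: "This follow-up may be conducted by phone for these participants and investigation participation for these participants will end upon completion of this follow-up" (CIP 6.4.1). On safety data, CIP 8 says: "Events and the status thereof will be collected through the final investigation required participant follow-up visit or premature discontinuation".

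**The concern.** The SAP moves the exclusion cut-off from Day 30 to Day 25 without giving a reason, although the endpoint still runs to Day 30. Someone who leaves on Day 26 without an event is excluded under the CIP, but not under the SAP's primary analysis. The SAP's supportive analysis of the same endpoint sides with the CIP.

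The difference has a direction. An SAE by Day 30 counts whenever the participant leaves, so relaxing the cut-off can only add participants with no recorded event. That raises both the observed proportion and its lower bound, on a test that decides one of two co-primary endpoints. Where the third rule does not clearly apply, whoever programs the analysis must choose, and one of the choices favours the device.

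**Working it through.** **Inputs.**
- Type I error (SAP 2.4): "The Type 1 error is 0.05 (two-sided").
- Assumed rate (CIP 7.3): freedom from related SAEs "is estimated at 92.6% through 30 days based on pre-market data".
- Performance goal (CIP 7.3): "The PG is set at 82.6% using a 10% non-inferiority margin".
- Attrition (CIP 7.3): "The rate of attrition through 30 days is assumed to be 10" per cent, so 150 × 0.10 = 15 lost and 135 evaluable.

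**1. The plan's own figure.** The test passes when the Clopper-Pearson lower bound, the 0.025 quantile of Beta(s, n − s + 1) with s event-free of n, exceeds 0.826. At n = 135 this needs s ≥ 121, that is, at most 14 participants with an event. Power is P(X ≥ 121 | 135, 0.926) = 0.92501, which matches the stated figure of over 92.5%. The attained one-sided error is P(X ≥ 121 | 135, 0.826) = 0.0162.

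**2. Adding k event-free leavers from Days 25–29 as successes to 135 evaluable.**

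| With an event | k | n | Lower bound | Result |
|---|---|---|---|---|
| 10 | 0 | 135 | 86.80% | pass |
| 10 | 3 | 138 | 87.08% | pass |
| 14 | 0 | 135 | 83.21% | pass |
| 15 | 0 | 135 | 82.34% | fail |
| 15 | 2 | 137 | 82.58% | fail |
| 15 | 3 | 138 | 82.71% | pass |
| 16 | 5 | 140 | 82.10% | fail |
| 16 | 10 | 145 | 82.70% | pass |

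With 17 events, k would have to be 17, more than the 15 losses assumed.

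**3. How many such leavers.** The documents give no count. If attrition is spread evenly over 30 days (assumption), 15 × 5/30 = 2.5. The possible range is 0 to 15.

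**4. How often the boundary is met.** At n = 135 the chance of exactly 15 events is the difference between passing at 120 and at 121 event-free. That is 0.9581 − 0.9250 = 0.033 at the design rate and 0.0298 − 0.0162 = 0.014 at the performance goal.

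**5. Type I error.** Assume an even hazard and that all k leave at Day 25. Each is then recorded event-free with probability 1 − 0.174 × 25/30 = 0.855 instead of 0.826. Compared with full observation of the same n, one-sided error moves from 0.0232 to 0.0243 at k = 3 and from 0.0233 to 0.0268 at k = 10.

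**6. Participants without procedure success.** CIP 3 expects about 10. If their contacts fall evenly over Days 25–35 (assumption), 10 × 5/11 ≈ 4.5 are contacted before Day 30. The unobserved time is 10 × (5 + 4 + 3 + 2 + 1)/11 ≈ 13.6 participant-days. With an even hazard (assumption), the expected number of missed events is 13.6 × 0.074/30 ≈ 0.03 at the design rate and 13.6 × 0.174/30 ≈ 0.08 at the performance goal.

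**The case against.** **The effect sits on a knife-edge.** The verdict changes only at 15 events with at least three such leavers, or at 16 with at least ten. Two leavers, within the rough estimate, leave 15 events a fail. The k required also depends on the starting number: from 144 evaluable, where at most 15 events pass, one added success lets 16 pass (16 of 145 gives 82.70%). Much of this is the discreteness of the exact test. All of this stands, and it limits the weight of the point.

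**The SAP does not say that leavers on Days 25–29 are event-free.** Its third rule requires being in the investigation and past the 30-day visit. Someone who leaves without that visit fits none of the three rules; someone who attended it early and then left may be counted. This stands: the defect is an unresolved classification with one favourable reading, not a written rule that scores them as successes.

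**A visit-window cut-off may be deliberate.** A leaver on Days 25–29 has been observed for most of the period, and the Kaplan-Meier analysis would show any difference. But the SAP gives no justification, and the Kaplan-Meier analysis is not the pass/fail test.

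Three stronger readings are tempting and not supported:
- *The safety window closes at Day 25.* It does not: both documents count SAEs through Day 30, and only the exclusion cut-off moves.
- *Everyone not observed to Day 30 counts as event-free.* Event-free leavers before Day 25 are excluded under both documents.
- *The early exit of participants without procedure success is a SAP departure from the CIP.* CIP 6.5 sets their required follow-up at 30 ± 5 days. One contacted on Day 25 has completed follow-up and has not discontinued prematurely, so CIP 7.7.3 does not exclude them either. The gap is a visit-window limit shared by both documents.

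**Conclusion.** The two documents conflict on evaluability for a co-primary endpoint, and the SAP's primary and supportive analyses disagree with each other. Event-free leavers on Days 25–29 escape exclusion under the SAP and are left unclassified or counted as event-free; counting them can only help the device.

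The size is small. At the design rate the lower bound moves by about 0.3 percentage points with three such leavers, and the verdict changes only close to the boundary. The estimate of 2 to 3 leavers rests on even attrition, and the type I error figures on an even hazard with every leaver going at Day 25. The point is worth correcting because the endpoint is pass/fail and the correction is cheap, not because a wrong conclusion is likely.

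The unobserved days for participants without procedure success are a separate and smaller limitation, worth reporting but not a contradiction between the documents.

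**What to change.** 1. In SAP 5.1.1, replace the Day 25 cut with the CIP 7.7.3 rule: premature discontinuation before Day 30 without a device- or procedure-related SAE is not evaluable. The rule should stay tied to premature discontinuation. Requiring a last contact on or after Day 30 is not what the CIP says, and would drop participants who completed their required follow-up inside the visit window.
2. Correct the third bullet to refer to device- or procedure-related SAEs, and word it so that every remaining participant is classified, including those whose required follow-up has ended.
3. Report how many participants without procedure success completed their only follow-up on Days 25–29, and add a sensitivity analysis that treats those without an event as not evaluable.

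The cost is two edited SAP sentences and one extra analysis. Planned power stays at 92.5% with 135 evaluable, because that figure already removes the full 10% attrition. The evaluable number may fall by a few compared with the SAP's present rule. If the sponsor prefers Day 25, the SAP should justify the departure from the CIP, state how Days 25–29 are classified, and show the Day 30 result as a sensitivity analysis.

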#### 5.1.2 Primary Effectiveness Endpoint

The primary effectiveness endpoint of the clinical investigation is an effectiveness measure based on the number of interventions post creation to facilitate AVF use and / or maintain AVF use through the timepoint of the 6-month follow-up of the last active treated participant.

The primary effectiveness endpoint will be evaluated by the following hypothesis:

- H0: The number of interventions post creation to facilitate AVF use and / or maintain AVF use (Facilitation and / or Maintenance Interventions) per patient year (PY) of participants treated with the WavelinQTM EndoAVF System (RWE) is greater than or equal to that of the PG of 5 post creation facilitation and maintenance interventions / PY.
- H1: The number of interventions post creation to facilitate AVF use and / or maintain AVF use (Facilitation and / or Maintenance Interventions) per PY of participants treated with the WavelinQTM EndoAVF System (RWE) is less than that of the PG of 5 post creation facilitation and maintenance interventions / PY.

That is:

 $H_0$ : RWE  $\geq$  5 post creation facilitation and maintenance interventions / PY

H1: RWE < 5 post creation facilitation and maintenance interventions / PY

Rejection of the null hypothesis will signify that the number of interventions post creation to facilitate AVF use and / or maintain AVF use (Facilitation and / or Maintenance Interventions) per PY of AVFs created using the WavelinQTM EndoAVF System is less than the PG of 5 post creation facilitation and maintenance interventions / PY.

Facilitation and/ or maintenance intervention will be identified if:

On the Post-Procedure Intervention page, Date of Post Procedure Intervention is not NULL and before or on the cutoff date of the database lock, and Type of Intervention is checked as Facilitation and/ or Maintenance. Note in the event that there are multiple treatments performed during the same procedure driven by multiple reasons, each reason driving the intervention will be counted as a separate intervention.

For each participant, the number of interventions post creation to facilitate AVF use and / or maintain AVF use through the timepoint of the 6-month follow-up of the last active treated participant is expressed as:

(Number of observed facilitation and/or maintenance interventions \* 365) / Length of investigation duration (Days)

Length of investigation duration (Days) is from the date of index procedure to the cutoff date of database lock (cutoff date – date of index procedure +1). If a participant discontinued early, then the last date of available study data (including the unscheduled visit date) will be used to calculate the length of investigation duration (last date of

available study data – date of index procedure +1). If a participant's endoAVF has permanent abandonment the date of permanent abandonment will be used to calculate the length of investigation duration (permanent abandonment date – date of index procedure +1).

The primary effectiveness analysis will be conducted on the AT population after the last active treated participant completes their 6-month follow-up; by this time, all participants still in the clinical investigation will have at least 6-months of data. The number of Facilitation and / or Maintenance Interventions per PY will be estimated by Poisson regression model with only the intercept term, and the estimate and 95% CI will be provided using the Wald method, and the p-value comparing to the PG will be calculated by a Chi-square test. The analysis will be repeated on the PP population.

